#### **3.2a Primary objectives**

- To determine the number of patients presenting with a diagnosis of LPD, screened for eligibility, who satisfy the eligibility criteria
- To determine the recruitment rates of eligible participants
- To determine the acceptability of the intervention to participants by using an internally designed patient satisfaction questionnaire and measuring the participant attrition rate (% of patients who fail to complete follow up data collection at 3 months)

- To determine participant adherence by measuring the proportion of scheduled physiotherapy sessions attended and prescribed exercise sessions completed by participant self-reporting

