### **SECTION 4.4 Outcomes**

#### **4.4a Primary outcomes**

- Eligibility defined as the % of participants with a diagnosis of LPD, screened for eligibility, who satisfy the eligibility criteria
- Recruitment rates defined as the % of eligible participants who consent to participate in the study
- Acceptability defined as the % attrition rate (participants who fail to complete follow up data collection at 3 months) and participant response to a patient satisfaction questionnaire
- Adherence defined as the % of scheduled physiotherapy sessions attended and participant self-reported intervention adherence defined as the % of prescribed exercise sessions completed

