## **SECTION 5 METHODS: DATA COLLECTION, MANAGEMENT, AND ANALYSIS**

### **SECTION 5.1 Data collection methods**

#### **5.1a Outcomes and time points at which they will be assessed**

Outcome	Measurement	Time point
Demographics	Age, sex, height, weight, affected knee, mechanism of injury (traumatic/atraumatic), previous history of ipsilateral patella dislocation, previous history of contralateral patella dislocation,	Baseline

	time from injury to presentation to acute care (ED or trauma services), family history of patella dislocation, employment status, level of education, ethnicity	
Assessment findings	
Presence/absence of the following on:
 
 
• A convincing patient history of a visible deformity on the lateral aspect of the knee or a sensation of the patella ‘popping’ out of joint followed by spontaneous reduction
 
• Presence of a haemarthrosis or joint effusion on clinical examination
 
• Tenderness along the medial patellofemoral complex (tenderness at the following bony landmarks or at any point extending between these two points: at or just proximal to the medial epicondyle of the femur and the midpoint of the medial aspect of the patella extending to the junction of the medial quadriceps tendon and the patella)
 
• Apprehension on laterally directed force of the patella
 
	Baseline
Eligibility	% of participants with a diagnosis of LPD who meet the eligibility criteria	Completion of study
Recruitment	
% of eligible participants who consent to participate in the study
 
Reasons for not consenting will also attempt to be collected
	Completion of study
Adherence	% of scheduled physiotherapy sessions attended	
Completion of intervention
 
3 months post first

	Participant self-reported % of prescribed home exercise sessions completed	physiotherapy session
Acceptability	% attrition rate  Patient satisfaction questionnaire	Completion of study  3 months post first physiotherapy session
Follow up	% of participants who consent to treatment who return 3 month questionnaires	Completion of study
Knee function, pain and instability	Lysholm Knee Scoring Scale	Baseline, 3 months post first physiotherapy session
Activity level	Tegner Activity Scale	Baseline, 3 months post first physiotherapy session

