### **5.1c Follow up data collection**

Follow up data collection will take place 3 months after the first physiotherapy session. For participants whose final physiotherapy appointment is within 1 week of this time, questionnaires will be administered after this appointment. Follow-up data collection for all other participants will be via postal questionnaire.

At least one reminder, via telephone or email, will be sent to participants who do not return postal questionnaires. Telephone or email contact will be used to obtain a score if follow up data collection is subsequently identified as being incomplete.

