### **5.2b Data storage during and after the study**

All study documents will be stored securely in locked filing cabinets accessible by study staff and authorised personnel only. Any personal details (e.g. addresses for postal questionnaires) will be held separately to outcome data. Electronic data will be password protected and stored on computers with swipe card access for authorised personnel only.

Follow-up outcome data will be collected from participants via stamped pre-addressed envelope to *CF* at the physiotherapy trauma outpatient department at the John Radcliffe Hospital

Any study related data transferred from *CF* to his supervisors will refer to participants by their unique code/number only and be transferred using an encrypted memory stick device. This data will be deleted as soon as it is no longer needed.

Personal data will be stored for up to 12 months after the study and then destroyed. Anonymised research data will be stored securely at City, University of London for 10 years after the study has finished.

Oxford University Hospital NHS Foundation Trust will collect information participant information from their medical records for this research study in accordance with our instructions. Oxford University Hospital NHS Foundation Trust will use the participant's name, NHS number and contact details to contact participants about the research study, make sure that relevant information about the study is recorded for their care, and to oversee the quality of the study. Individuals from City, University of London and regulatory organisations may look at the participant's medical and research records to check the accuracy of the research study. Oxford University Hospital Foundation Trust will pass these details to City, University of London along with the information collected from the participant and/or their medical records. The only people in City, University of London who will have access to information that identifies participants will be people who need to contact the participants to monitor the conduct of the study or audit the data collection process. The people who analyse the information will not be able to identify participants and will not be able to find out the participant's name, NHS number or contact details.

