## **SECTION 7.5 Declarations of interests**

*CF* is in receipt of a MRes Clinical Research NIHR Studentship Award and employed by Oxford University Hospital Foundation Trust as a band 6 trauma outpatient physiotherapist. Competing interests: none.

*MH* is supported by the NIHR (NIHR Programme Grants for Applied Research RPPG-1210-12011) Competing interests: none.

*SH* is supported by City, University of London and has funding for research from the Bart's Charity, NIHR RfPB scheme, and the EPSRC. Competing interests: none.

*DK* is supported by the NIHR (NIHR Post Doctoral Fellowship, [name], PDF-2016-09-056). Competing interest: none.

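### Satisfaction forms are completed after the last appointment or posted to the lead investigator at the treating department, which creates a risk of courtesy bias in the primary acceptability outcome

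*Combined protocol and SAP*

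**What the plan says.** **The outcome.** Section 4.4a defines acceptability by 3-month attrition and by "participant response to a patient satisfaction questionnaire". Section 3.2a calls the instrument an "internally designed patient satisfaction questionnaire". The plan gives no weights for the two components and describes neither the items nor any validation. The table in 5.1a places the questionnaire 3 months after the first physiotherapy session.

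**The two routes.** Section 5.1c says: "For participants whose final physiotherapy appointment is within 1 week of this time, questionnaires will be administered after this appointment". It continues: "Follow-up data collection for all other participants will be via postal questionnaire". Non-returners of postal forms get at least one reminder, and incomplete follow-up is completed by telephone or email. The caller is not named.

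**Where the forms go.** Section 5.2b says: "Follow-up outcome data will be collected from participants via stamped pre-addressed envelope", addressed to the lead investigator at the physiotherapy trauma outpatient department. Patients who cannot attend that department for treatment are excluded (4.2a). Section 7.5 describes the lead investigator as "employed by Oxford University Hospital Foundation Trust as a band 6 trauma outpatient physiotherapist". Section 5.2a has the lead investigator enter the paper questionnaires into the database.

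**Safeguards.** Forms carry a subject code only (5.2a, 7.4). Personal details are kept apart from outcome data, paper is locked away with restricted access, and analysts are said to be unable to identify participants (5.2b).

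**Analysis.** Section 5.3a is descriptive: median and inter-quartile range for ordinal satisfaction data, counts and percentages for categorical data. Section 3.2 sets no numerical targets.

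**The concern.** Participants are asked to judge a treatment either after their last session or in a letter to the department that treated them. People tend to be polite about staff who have just helped them, so any distortion would probably run upward. The lead investigator is also visible to participants: contact details go out with the information packs (4.7a), and the lead investigator contacts those who withdraw or do not adhere (5.1d).

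Acceptability is central to the study. Section 3.1b reads the 52% attrition in the earlier exercise trial as a sign that parts of its design were not acceptable, and gives this as the reason for measuring acceptability before a definitive trial. An instrument for that purpose has to make dissatisfaction easy to express. With one group there is no second arm in which the same inflation would appear and cancel.

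Route is also mixed with engagement. Those who complete the form after an appointment are by definition still attending close to 3 months.

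**Working it through.** **1. Follow the form.**

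| Step | After-appointment route | Postal route |
|---|---|---|
| Who | Final appointment within 1 week of 3 months (5.1c) | Everyone else (5.1c) |
| Completed | After that appointment; place and administrator not stated | Away from the appointment |
| Returned to | Not stated | Lead investigator, treating department (5.2b) |
| Entered by | Lead investigator (5.2a) | Lead investigator (5.2a) |

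On neither route does the readable text provide a sealed or independent return, exclude the treating physiotherapist from the room, tell the participant who will see the answers, or report satisfaction by route. Coding protects confidentiality in storage. It does not change what a participant is willing to write, and reminders require someone to link code to person.

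**2. The plan's own figures.** There is no satisfaction figure to reproduce. The one derived count in 4.6a does reproduce (31 + 23 = 54 per year; 54/2 = 27 in 6 months), but nothing here depends on it. The target of 15 is described as pragmatic, without a power calculation.

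**3. Size, by illustration only.** The share completing after an appointment, the response scale and any expected shift are not given. Suppose satisfaction were reduced to a proportion with true value p, a share s used the after-appointment route, and courtesy raised the proportion by d_A on that route and d_P by post:

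observed = s(p + d_A) + (1 − s)(p + d_P), so bias = s·d_A + (1 − s)·d_P.

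For assumed p from 60% to 80%, no cell reaches the 100% ceiling and p drops out. Bias in percentage points:

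| s | d_A = 10, d_P = 0 | d_A = 20, d_P = 0 | d_A = 20, d_P = 10 |
|---|---|---|---|
| 25% | 2.5 | 5.0 | 12.5 |
| 50% | 5.0 | 10.0 | 15.0 |
| 75% | 7.5 | 15.0 | 17.5 |

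The range is 2.5 to 17.5 points, or 15 × 0.025 = 0.4 to 15 × 0.175 = 2.6 of 15 participants. With d_A = d_P = 0 the bias is zero.

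**4. Against sampling error.** If 12 of 15 were satisfied, the exact (Clopper-Pearson) 95% interval would be 51.9% to 95.7%. The illustrated bias lies well inside that width, so the data could not reveal it. Splitting by route does not help as a test: 6 of 7 satisfied on one route has an interval of 42.1% to 99.6%.

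**5. On the planned summary.** With 15 ordinal responses the median is the 8th in order. Upgrades by participants already at or above it leave it unchanged, so a few kinder answers may not move the reported figure.

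**The case against.** The strongest reply is that nothing in the documents shows bias, and that its consequence is limited. The analysis is descriptive, no target is set, and satisfaction is read beside attrition, attendance and exercise completion. Completing forms at an appointment and chasing by telephone also protect return rates, which matters with 15 participants and a predecessor that lost 52%. All of this stands. It limits the strength of the point and the shape of the remedy, but it does not justify leaving the return route as it is.

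Several stronger readings are tempting and should be resisted:

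- *That satisfaction will be inflated.* Upward is the likely direction, but the documents support only a risk.
- *That the lead investigator is one of the people being rated.* Section 4.2b says HCPC-registered physiotherapists deliver the treatment. The readable text does not say whether the lead investigator is among them; employment as a trauma outpatient physiotherapist does not settle it. The contributorship section (1.5a in the contents list) is not in the text available, so it may say.
- *That nothing separates the answers from treating staff.* Coding, separate storage and restricted access exist. They are weak here, because the lead investigator receives and enters the forms, but they are not nothing. Who holds the code key and who makes the calls is not stated.
- *That the effect is 6.7 points per participant.* 1/15 = 6.7% is the step size of a proportion with 15 respondents. It measures granularity and is not evidence of bias, and a percentage satisfied is not a defined outcome.
- *That satisfaction is half of the outcome.* It is one of two components, with no weighting.
- *That completion at an appointment or by telephone should be banned.* This trades a possible bias against missing data, and the documents do not settle that trade in favour of a ban.

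**Conclusion.** The point holds as a risk: the way satisfaction forms are collected could make the intervention look more acceptable than it is, and nothing planned would show it. The collection facts are firm. The size is unknown; 2.5 to 17.5 percentage points holds only under the assumed shares and shifts above, and zero is also compatible with the documents. The direction rests on the general assumption that people are courteous to those who treated them. Since no numerical target is set, no decision rule depends on the result; what is at stake is how far a favourable satisfaction summary can be believed when the next study is designed. It is a cheap improvement to a primary outcome component and does not affect the sample size.

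**What to change.** Amend 5.1c and 5.2b so that the satisfaction form is handled separately from the PROMs:

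- Participants complete it in clinic or at home, without the treating physiotherapist present.
- They seal it, marked with the code only, in an envelope addressed to an academic supervisor at the sponsor and not to the treating department.
- The form states that treating staff will not see individual answers. Section 5.2a needs a matching line on who enters these answers, because it now assigns entry of all paper questionnaires to the lead investigator, and the statement must be true.
- Missing satisfaction items are chased by someone outside the treating department, or left missing and reported under 5.3b.
- Satisfaction is reported by collection route with the number returned, as description and not as a test for bias.
- Attrition at 3 months is judged on the PROMs, so that a lower satisfaction return does not raise it.

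The cost is a second envelope, a sentence on the form, slightly more handling, and possibly a few more missing satisfaction items. A supervisor who is also a protocol author is not fully independent, but is outside the treating department.

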### **5.1d Retention**

Participants will be informed their participation is voluntary and they can withdraw at any time with no obligation to explain why and without affecting the quality of their care. CF will attempt to contact participants who wish to withdraw, or do not adhere to the exercise intervention, to determine if they are willing to participate in follow up data collection. Participants who withdraw from treatment but participate in data collection will not be

considered withdrawals. Participant data prior to withdrawal will be used unless the participant expressly refuses consent to use of this data. The reason to withdraw, if provided, will be recorded on the study withdrawal case report form. Participants may be withdrawn after enrolment by the authors if it is subsequently determined they do not meet the eligibility criteria.

## **SECTION 5.2 Data management**

### **5.2a Data entry**

Each participant will be assigned a unique subject code/number. All study documents, except the signed consent form and contact details for postal questionnaires, will refer to the patient by their unique subject code/number only.

Data from paper questionnaires, case reports forms and treatment logs will be entered by *CF* into an electronic database that will be password protected, and on computers at the John Radcliffe hospital, that are swipe card access for NHS employees only.

Study personnel collecting data will be provided with detailed written information outlining how to record and store outcome data. This will include how to complete case reports forms, advice to complete case report forms in ink, to avoid use of correction fluid, the normal range of values where appropriate and how to store case report forms on site.

Standard physiotherapy notes will be made in accordance with standard local practice and documented on the local electronic notes system (EPR). These will not include any data recorded for the study that is not routinely collected during standard practice.

### **5.2b Data storage during and after the study**

All study documents will be stored securely in locked filing cabinets accessible by study staff and authorised personnel only. Any personal details (e.g. addresses for postal questionnaires) will be held separately to outcome data. Electronic data will be password protected and stored on computers with swipe card access for authorised personnel only.

Follow-up outcome data will be collected from participants via stamped pre-addressed envelope to *CF* at the physiotherapy trauma outpatient department at the John Radcliffe Hospital

Any study related data transferred from *CF* to his supervisors will refer to participants by their unique code/number only and be transferred using an encrypted memory stick device. This data will be deleted as soon as it is no longer needed.

Personal data will be stored for up to 12 months after the study and then destroyed. Anonymised research data will be stored securely at City, University of London for 10 years after the study has finished.

Oxford University Hospital NHS Foundation Trust will collect information participant information from their medical records for this research study in accordance with our instructions. Oxford University Hospital NHS Foundation Trust will use the participant's name, NHS number and contact details to contact participants about the research study, make sure that relevant information about the study is recorded for their care, and to oversee the quality of the study. Individuals from City, University of London and regulatory organisations may look at the participant's medical and research records to check the accuracy of the research study. Oxford University Hospital Foundation Trust will pass these details to City, University of London along with the information collected from the participant and/or their medical records. The only people in City, University of London who will have access to information that identifies participants will be people who need to contact the participants to monitor the conduct of the study or audit the data collection process. The people who analyse the information will not be able to identify participants and will not be able to find out the participant's name, NHS number or contact details.

City, University of London is the data controller for the personal data collected for this research project. Participant personal data will be processed for the purposes outlined in this notice. The legal basis for processing participant personal data will be that this research is a task in the public interest.

## **SECTION 5.3 Statistical methods**

### **5.3a Statistical Methods for analysing primary and secondary outcomes**

Statistical methods and results will be reported, where possible, in accordance with SAMPL guidelines. All analyses will be conducted using the latest version of SPSS (IBM Corp. Armonk, NY).

Eligibility, recruitment, acceptability and adherence will be described using descriptive statistics and expressed as integers and percentages where relevant.

Tegner Activity scores will represent ordinal data. Baseline and 3 months post 1st physiotherapy session scores will be described using descriptive statistics using median and inter-quartile range.

Lysholm scores will represent continuous data. Baseline and 3 months post 1st physiotherapy session scores will be described using descriptive statistics using mean and standard deviations if scores are normally distributed or median and inter-quartile range if data is skewed.

EQ-5D-5L scores will represent continuous data. Baseline and 3 months post 1st physiotherapy session scores will be described using descriptive statistics using mean and standard deviations if scores are normally distributed or median and inter-quartile range if data is skewed.

Patient satisfaction scores will be described using descriptive statistics. Ordinal data will be expressed using medians and inter-quartile ranges, and categorical data will be expressed as integers and percentages.

Baseline characteristics and additional outcome data on intervention delivery and harms will be expressed using descriptive statistics. Continuous variables will be described using means and standard deviations for normal distributions or medians and inter-quartiles range for non-normal distributions. Categorical data will be expressed as integers and percentages.

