#### **4.3b Intervention – concomitant care**

As the efficacy of the intervention is not in question, concomitant health care such as medication use will not be recorded, and other aspects of care will continue as usual.

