#### **4.4b Secondary outcomes**

- Acceptability of outcome data collection by participants defined as the % completion of the PROMs outlined below.
- The Tegner Activity Scale measures activity on a scale from 0-10, with higher scores indicating higher activity. It has shown good reliability and content validity in patients with acute patellar dislocation and prior dislocation/subluxation and shown to measure a distinct aspect of recovery demonstrated by its low correlation with knee specific and general health questionnaires in this cohort. It has previously been used to assess the effect of conservative management in patients with first

time LPD patients. It will be completed after informed consent has been obtained prior to the first physiotherapy session based on **pre-injury** activity levels and at 3 months after the first physiotherapy session based on their activity levels at that time. It will be administered as a patient completed questionnaire. The change in Tegner Activity Scale scores will be used for analysis.

[figure not shown]
- The Lysholm Knee Scoring Scale was originally developed for patients with knee ligament injuries and subsequently revised. It is scored from 0-100 with lower scores indicating higher pain and disability. It has since demonstrated good test-retest reliability in patients with first time LPD and prior subluxation/dislocation and was able to discriminate between those who subsequently developed recurrent instability and those who did not. It has been used to assess the effect of conservative management in patients with first time LPD and recurrent LPD. It will be completed after informed consent has been obtained prior to the first physiotherapy session and 3 months after the first physiotherapy session based on **current** knee symptoms at that time. It will be administered as a patient completed questionnaire. The change in Lysholm Knee scores will be used for analysis.
- The EQ-5D is a commonly used quality of life questionnaire. It will be completed after informed consent has been obtained prior to the first physiotherapy session and 3 months after the first physiotherapy session based on **current** symptoms at that time. It will be administered as a patient completed questionnaire. The change in EQ-5D scores will be used for analysis.

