### **5.3b Missing data**

Missing data for each questionnaire and item level missingness will be reported to help select future study outcome instruments.

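### Section 4.4b makes change in Tegner, Lysholm and EQ-5D the quantity analysed, but section 5.3a summarises each visit separately and names no paired analysis set

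*Combined protocol and SAP*

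**What the plan says.** Section 4.4b closes its description of each instrument with the same kind of statement: "The change in Tegner Activity Scale scores will be used for analysis"; "The change in Lysholm Knee scores will be used for analysis"; "The change in EQ-5D scores will be used for analysis". It also sets the reference points. Baseline Tegner refers to activity before the injury, while baseline Lysholm and EQ-5D refer to the participant's state at that time.

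Section 5.3a gives the method. For Tegner, the baseline and three-month "physiotherapy session scores will be described using descriptive statistics using median and inter-quartile range". For Lysholm, and in the same terms for EQ-5D-5L, the two sets of "scores will be described using descriptive statistics using mean and standard deviations if scores are normally distributed or median and inter-quartile range" if skewed. The closing general paragraph of 5.3a covers baseline characteristics, intervention delivery and harms. The outcome table in 5.1a lists instruments and time points. Neither mentions change.

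On missing data, section 5.3b says: "Missing data for each questionnaire and item level missingness will be reported to help select future study outcome instruments". It does not say whose scores enter each summary.

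Two statements set the weight of the point. Section 4.3b says: "As the efficacy of the intervention is not in question". Section 3.2b lists completion of the questionnaires as an objective, not change in their scores.

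For the feasibility outcomes, 5.3a says: "Eligibility, recruitment, acceptability and adherence will be described using descriptive statistics and expressed as integers and percentages where relevant". It names no interval. Section 3.2 states that no numerical feasibility targets were set.

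**The concern.** An analysis announced in one section has no method in the section that should supply it. A report that followed 5.3a to the letter would print two columns, baseline and three months, and readers would subtract one from the other. That subtraction is not in general the within-person change. If some participants do not return the three-month questionnaire, it also compares different groups of people. Loss is a realistic prospect: section 3.1b cites 52% attrition in the one published randomised comparison of exercise programmes for this injury.

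The Tegner column needs particular care. Its baseline is the pre-injury level, so a fall means that activity has not yet returned to that level. It does not mean deterioration under treatment.

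A related gap concerns precision. With no targets to judge against, what this study hands on is a set of estimates. Bare percentages from about 15 people do not show how uncertain those estimates are.

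**Working it through.** The plan gives no figure for change, and no alpha, power or SD, so there is nothing to reproduce. The checks ask what can be recovered from the planned summaries.

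**1. The two sections side by side**

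| Instrument | 4.4b: quantity analysed | 5.3a: planned summary | Paired set named? |
|---|---|---|---|
| Tegner | change from pre-injury level | median and IQR at each visit | no |
| Lysholm | change from status at enrolment | mean and SD, or median and IQR, at each visit | no |
| EQ-5D-5L | change from status at enrolment | mean and SD, or median and IQR, at each visit | no |

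**2. Median and IQR (invented Tegner-like scores)**

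- *Eleven pairs.* Baseline 3, 4, 4, 5, 5, 6, 6, 7, 7, 8, 9 (median 6). Three months 2, 3, 3, 4, 4, 4, 5, 5, 6, 6, 7 (median 4). The difference of medians is 4 − 6 = −2. Paired in rank order, the differences are −1 seven times and −2 four times, so the median change is −1.
- *Fifteen pairs.* Baseline 3, 4, 4, 5, 5, 6, 6, 6, 7, 7, 7, 8, 9, 9, 9 (median 6, IQR 5 to 7.5). Three months 1, 2, 2, 3, 3, 3, 4, 4, 4, 5, 5, 6, 6, 7, 9 (median 4, IQR 3 to 5.5). Both sets were held fixed and re-paired at random 200,000 times. The median change ranged from −4 to 0, and 124,022 pairings (62%) gave −2.
- *Spread in the same fifteen.* Rank-order pairing gives an IQR of change of −2 to −2, with 14 of 15 lower. Reverse-order pairing gives −4.5 to 0.5, with 10 lower and 4 higher. The visit summaries are identical in both.

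**3. Mean and SD**

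If the same people contribute at both visits, mean change = mean at three months − mean at baseline, so the mean change is recoverable. Its SD is not:

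SD(change) = √(SD₀² + SD₁² − 2ρ·SD₀·SD₁).

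The documents give no correlation ρ. With equal SDs (assumed), SD(change) = SD·√(2(1 − ρ)). This is 1.41 SD at ρ = 0, 1.00 at 0.5, 0.77 at 0.7 and 0.45 at 0.9. The 95% half-width for mean change at n = 15, t × SD(change)/√15 with 14 degrees of freedom, runs from 0.78 SD (ρ = 0) to 0.25 SD (ρ = 0.9). That is about a threefold range.

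**4. Different people at the two visits**

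Suppose k of n are lost, their baseline mean is g below that of completers, and nobody changes. The two visit means then differ by (k/n) × g.

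- k = 3, n = 15, g = 10: 2.0 points.
- k = 4, n = 15, g = 10: 2.7 points; g = 20: 5.3 points.
- 52% attrition: 0.52 × 15 = 7.8, about 8 lost; g = 10 gives 8/15 × 10 = 5.3 points.

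The gap g is an assumption throughout.

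**5. Precision of the feasibility percentages (Clopper–Pearson, 95%)**

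| Illustration | Estimate | Interval |
|---|---|---|
| 27 of 47 eligible | 57.4% | 42.2–71.7% |
| 15 of 27 consenting | 55.6% | 35.3–74.5% |
| 3 of 15 lost | 20.0% | 4.3–48.1% |
| 4 of 15 lost | 26.7% | 7.8–55.1% |
| 11 of 15 questionnaires complete | 73.3% | 44.9–92.2% |

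The 27 is half of the 54 eligible per year in 4.6a. The 47 is half of the 94 patients in 3.1a, assuming that both counts share one base. The 15 is the target. The numbers lost and complete are invented.

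**6. Consent percentage and recruitment time (optional item)**

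Section 4.6a gives 31 patients known to be eligible, an estimate of 54, and 31 + 51 = 82 if every unknown were eligible. At 15/27 uptake:

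- 31/12 × 15/27 = 1.44 recruits per month (8.6 in 6 months).
- 54/12 × 15/27 = 2.50 per month (15 reached at 6.0 months).
- 82/12 × 15/27 = 3.80 per month (15 reached at about 4 months).

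For an assumed 100 recruits at one such site, that is 69.7, 40.0 or 26.3 months under the same consent percentage.

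**The case against.** The case for leaving the plan alone is respectable. Section 5.3a does not exclude a change score; it is silent, so this is incomplete specification more than flat contradiction. The formal secondary outcome is questionnaire completion, and no test or sample size depends on change. Section 5.3b will show how many scores are missing, and 5.1b and 5.1c provide for chasing incomplete data. Counts will be reported, so a reader can compute any interval. Sections 5.3a and 7.8a also commit to SAMPL (where possible) and to the CONSORT extension for pilot and feasibility trials.

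Most of this stands and limits the weight of the point. It does not supply the missing method. Reporting how many scores are absent does not produce a summary in people who have both, and the two reporting commitments, as written here, specify neither a change summary nor an interval.

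Three stronger readings are tempting, and the documents do not support them.

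- *Within-person change is lost.* It is not. Section 5.2a has data entered under a unique participant code, so change can be computed. Under mean and SD reporting, the mean change even follows from the visit means when the same people contribute to both.
- *The study would be drawing an efficacy conclusion from change.* Section 4.3b says that efficacy is not in question, and no objective concerns score change.
- *The consent percentage is a wrong definition of recruitment.* It is a valid one. Section 3.1b says only that recruitment rates will help in estimating duration; the number eligible is a primary objective and a six-month window is stated. The monthly rate is unclear only if recruitment stops early and the date is not reported.

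**Conclusion.** The mismatch between 4.4b and 5.3a holds for all three instruments, and no other section resolves it. It should be reconciled before analysis, but it is a modest point: the planned reporting is incomplete, while the data and the primary outcomes are unaffected.

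That visit medians and IQRs do not determine the median or spread of change, and that visit SDs do not determine the SD of change, needs no assumption about this trial. The sizes do. The Tegner scores, the number lost, the 10 to 20 point Lysholm gap and the correlations are illustrative, so they show what could happen and are not forecasts.

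Adding intervals is a worthwhile free improvement, because percentages on about 15 people are very imprecise. Reporting recruitment over time is optional and corrects no error; its spread of 26 to 70 months takes the extreme cases in which all or none of the 51 patients of unknown eligibility qualify.

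**What to change.** Reconcile the two sections in one of two ways.

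- **Preferred.** Add to 5.3a, for each instrument, the within-person change in participants with both scores, together with the number of pairs. Use median and IQR for Tegner, labelled as relative to the pre-injury level. Use mean and SD, or median and IQR if skewed, for Lysholm and EQ-5D-5L. State that these are descriptive secondary summaries and not an efficacy analysis.
- **Alternative.** If change is not wanted, delete the three statements in 4.4b.

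In the same edit, report numerator, denominator and a 95% interval by one named method (exact or Wilson) for eligibility, recruitment, attrition and questionnaire completion.

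Optionally, because 4.6a allows recruitment to end before six months, report the actual start and stop dates and the eligible and consented participants per month beside the consent percentage. This would support the use described in 3.1b.

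The cost is a few lines of text, with no new data and no more participants.
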